## 10.5. Appendix 5: Derived and Transformed Data

### 10.5.1. General

#### Multiple Measurements at One Time Point

- Mean of the measurements will be calculated and used in any derivation of summary statistics but if listed, all data will be presented.
- Unscheduled visit will be included in the listings.

#### Study Day

- Calculated as the number of days from the first study treatment date for mothers :
  - [1] Ref Date = Missing → Study Day = Missing (none displayed)
  - [2] Ref Date < First Study Treatment Date → Study Day = Ref Date – First Study Treatment Date
  - [3] Ref Date ≥ First Study Treatment Date → Study Day = Ref Date – First Study Treatment Date + 1

Note: All assessments should be done after the first study treatment date for mothers.

## 10.6. Appendix 6: Premature Withdrawals & Handling of Missing Data

### 10.6.1. Premature Withdrawals

Element	Reporting Detail
General	

• Subject study completion status is defined as subjects who are prematurely withdrawn.

• Subjects who are withdrawn from study participation after enrolment in ARIOS study will not be replaced.

### 10.6.2. Handling of Missing Data

Element	Reporting Detail
General	

• Missing data occurs when any requested data is not provided, leading to blank fields on the collection instrument :

[1] These data will be indicated by the use of a “blank” in subject listing displays.

[2] Answers such as “Not applicable” and “Not evaluable” are not considered to be missing data and should be displayed as such.

• For disposition and demographic data, no imputation will be done.

• For safety and neurodevelopment data, it will be assumed that the events of interest did not occur.

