7. The CBCL/1.5–5 and M-CHAT-R/F questionnaires will be completed for all infants. The completion window for the CBCL/1.5–5 and M-CHAT-R/F is +6 weeks at 18 months (M-CHAT-R/F only) and +12 weeks at 24 months.
8. Referral will be made for infants who score in the black zone for the gross motor skills domain on the 24-month corrected age ASQ-3 and do not have an existing diagnosis of cerebral palsy.

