6.2.5.1. The ASQ-3 Score Interpretation and Possible Specialist Referral Recommendations

The ASQ-3 scores for this study will be interpreted and recommendations will be offered according to the following:

[figure not shown]
- The child’s development will be considered to be on schedule if the child’s ASQ-3 scores are in the white zone (higher than 1 SD below the mean), and no further action is required.
- If the child’s ASQ-3 scores are in the grey zone (≤ 1 SD below the mean), the parent/legal guardian may share the ASQ-3 test results with the child’s HCP.

- If any of the child's ASQ-3 scores are in the black zone (≥ 2 SD below the mean), then the child's parent/legal guardian will be asked if the child is already under the care of a developmental specialist who can or has made a formal assessment (e.g., using the BSID-III). If a recent (≤ 3 months) BSID-III was conducted, the BSID-III will not be repeated and the RCC-PI will request results from the relevant HCP. If the child is not currently under the care of a developmental specialist, then the parent/legal guardian will be referred to a qualified assessor for developmental evaluation (e.g., using the BSID-III), and a neurologic examination will be conducted, if indicated.
- BSID-III retesting will be performed if the child's ASQ-3 scores are in the black zone on a subsequent ASQ-3 test following the first BSID-III referral.
- If, at 24 months corrected age, the child's ASQ-3 gross motor domain score is in the black range and the child has not already been diagnosed with cerebral palsy, the parent/legal guardian will be referred to a qualified examiner for a formal assessment to determine if this condition is present.

Reports from all specialists will be included in the subject's source documents. For further details regarding the ASQ-3 refer to the SPM.

An overview for the collection and review of data for the ASQ-3 is provided in [Figure 3](#).

Figure 3 ASQ-3, M-CHAT-R/F, and CBCL/1.5–5: Flow Chart of Data Collection and Review

ASQ-3 = Ages and Stages Questionnaire-3; BSID-III = Bayley Scales of Infant Development, third edition; CBCL/1.5–5 = Child Behavior Checklist for ages 1.5 to 5; HCP = health care provider; M-CHAT-R/F = Modified Checklist for Autism in Toddlers-Revised with Follow-Up; RCC-PI = research coordinating center-principal investigator.

1. A neurologic examination will also be conducted, if indicated.

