6.2.6. Overall Measure of Neurodevelopmental Impairment

- Proportion of infants with at least 1 of the following indicators of neurodevelopmental impairment:
 - Hearing impaired, uncorrected even with aids (at 24 months chronological age)
 - Blindness in 1 or both eyes, or sees light only (at 24 months chronological age)
 - Cerebral palsy (moderate defined as grade 2 or 3 and severe defined as grade 4 or 5 using the Gross Motor Functional Classification System [GMFCS]) (at 24 months corrected age)

- Cognitive impairment: BSID-III Cognitive Scale Score of >2 SDs below mean score (<4) (at 24 months corrected age)
- Motor impairment: BSID-III Motor Composite Scale Score of >2 SDs below mean score (<70) (at 24 months corrected age)
- Diagnosis of ASD, ADD, or ADHD

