	
 
• Neurodevelopment endpoints assessed at ages 9, 18, and 24 months, corrected for prematurity: 
 
• Proportion of infants with an ASQ-3 score in the black zone in any domain
 
• Proportion of infants with an ASQ-3 score in the black zone for gross motor skills
 
• Proportion of infants with an ASQ-3 score in the black zone for fine motor skills
 
• Proportion of infants with an ASQ-3 score in the black zone for communication
 
• Proportion of infants with an ASQ-3 score in the black zone for problem-solving
 
• Proportion of infants with an ASQ-3 score in the black zone for personal-social skills
 
• Proportion of infants referred for developmental evaluation (using BSID-III)
 
• Proportion of infants with a BSID-III score <math>>2</math> SDs below the mean score for the cognitive scale (<math><4</math>)
 
• Proportion of infants with BSID-III score <math>>2</math> SDs below the mean score for the gross motor scale (<math><4</math>)
 
• Proportion of infants with BSID-III score <math>>2</math> SDs below the mean score for the fine motor scale (<math><4</math>)
 
• Proportion of infants with a BSID-III score <math>>2</math> SDs below the mean score for the language scale (<math><70</math>)
 
• Proportion of infants with a CBCL/1.5-5 score above the 97th percentile for a subset of prespecified questions that relate to attention and hyperactivity problems
 
• Proportion of infants indicated as needing further evaluation after completion of the M-CHAT-R/F
 
• Proportion of infants referred for neurological evaluation to determine diagnosis of cerebral palsy
 
 
 
• Proportion of infants with at least 1 of the following indicators of neurodevelopmental impairment: 
 
• Hearing impaired, uncorrected even with aids (at 24 months chronological age)
 
• Blindness in 1 or both eyes, or sees light only (at 24 months chronological age)
 
• Cerebral palsy (moderate and severe) (at 24 months corrected age)
 
• Cognitive impairment: BSID-III Cognitive Scale Score of <math>>2</math> SDs below mean score (<math><4</math>) (at 24 months corrected age)
 
• Motor impairment: BSID-III Motor Composite Scale Score of <math>>2</math> SDs below mean score (<math><70</math>) (at 24 months corrected age)
 
• Diagnosis of ASD, ADD, or ADHD
 
 
 

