## **7.2.3. Neurodevelopment Assessment at 9, 18, and 24 months**

Neurodevelopment will be assessed by determining the proportions of infants diagnosed with developmental delays listed below at 9, 18, and 24 months of age, corrected for prematurity.

Endpoints related to Ages and Stages Questionnaire version 3 (ASQ-3) score and developmental evaluation described in Section 2.2 will be descriptively summarized at 9, 18, and 24 months by treatment group. For subjects with an ASQ-3 score in the black zone ( $\geq 2$  standard deviation [SD] below the mean) for any domain and referred for development evaluation, number of infants and percentage with Bayley Scales of Infant Development 3rd edition (BSID-III) and non-BSID-III results will be summarized. For subjects with an ASQ-3 score in the black zone for any domain, referred for development evaluation, but no assessment done, reason of no assessment done will be summarized. In addition to endpoints described in Section 2.2, number of infants and percentage with moderate or severe developmental delay using non BSID-III score will be summarized.

For BSID-III score, scaled scores for cognitive, receptive communication, expressive communication, fine motor, and gross motor will be derived from the subtest total raw scores and range from 1–19, with a mean of 10 and an SD of 3. Language composite scores will be derived from sums of receptive communication and expressive communication scaled scores. The composite score will be scaled to a metric with a mean of 100 and an SD of 15, and range from 40–160.

Endpoints related to Modified Checklist for Autism in Toddlers Revised with Follow-Up (M-CHAT-R/F) described in Section 2.2 will be descriptively summarized at 18, and 24 months by treatment group.

Endpoints related to Child Behavior Checklist for Ages 1.5 to 5 (CBCL/1.5-5) and cerebral palsy in Section 2.2 will be descriptively summarized at 24 months by treatment group.

Neurodevelopment assessment data will be presented in listings.

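### SAP 10.6.2 counts safety and neurodevelopment data that were requested but not obtained as no event, so unreturned screens and unassessed referrals can only lower the reported rates

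*SAP*

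**What the plan says.** SAP 10.6.2 defines the gap: "Missing data occurs when any requested data is not provided, leading to blank fields on the collection instrument". Answers such as not applicable or not evaluable "are not considered to be missing data and should be displayed as such". Disposition and demographic data are not imputed. For the rest, "For safety and neurodevelopment data, it will be assumed that the events of interest did not occur". No instrument is exempted.

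SAP 7.2 reports the number and percentage with each binary event and shows N as everyone in the treatment group. SAP 7.2.5 reports the 24-month impairment composite and its components as number and percentage.

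The assessments are staged. Under Protocol 6.2.5.1, a black-zone ASQ-3 score leads to a developmental evaluation, for example by BSID-III, unless a specialist is already involved. For cerebral palsy, Protocol Table 2, note 8, states: "Referral will be made for infants who score in the black zone for the gross motor skills domain on the 24-month corrected age ASQ-3", if there is no existing diagnosis. Referral is itself an endpoint (SAP 2.2), for example "Proportion of infants referred for neurological evaluation to determine diagnosis of cerebral palsy". SAP 7.2.3 foresees incomplete referrals: for children "referred for development evaluation, but no assessment done, reason of no assessment done will be summarized". It also counts moderate or severe delay found with tools other than the BSID-III.

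Protocol 3.2 warns that loss to follow-up is common in such studies and can bias ascertainment. Protocol 4.4 lets a family miss an assessment and stay in. Protocol 7.1.2 analyses children with some follow-up to the length of that follow-up, and states no non-event imputation.

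**The concern.** The neurodevelopment proportions and the composite are primary endpoints. No model or test is planned, so the percentages are the result. Protocol 1.2 gives the purpose as assurance that treatment is not linked to significant adverse outcomes. A rule that turns unknown into unharmed errs in one direction only, toward that conclusion.

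The assumption is weakest at the referral step, because a referred but unassessed child has just screened in the black zone. In a placebo group of six, one or two blanks change the rate visibly.

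**Working it through.** **Inputs from the documents.** Protocol Appendix 1 gives 6 placebo, 43 atosiban and 49 retosiban infants. Check: 6 + 43 + 49 = 98, and 98/(900 + 330) = 98/1230 = 7.97%, the stated 8%. The documents give no non-return rate, event rate or share of referrals left unassessed. **All rates and counts of missing children or events below are assumptions.**

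**Formulas.** Let N be infants in the arm, m those with the item missing, x events seen, and y the unknown events among the missing (0 to m).
- SAP rule: x/N
- Full data: (x + y)/N
- Observed cases: x/(N − m)
- Worst case: (x + m)/N

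Since y cannot be negative, x/N never exceeds the full-data rate and equals it only when y = 0. The SAP figure is therefore the best case, shown without its counterpart.

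**Same risk in missing children.** Shown rate = true rate × (1 − proportion missing). With 10%, 20% and 30% missing, a true 10% shows as 9%, 8% and 7%; a true 20% shows as 18%, 16% and 14%.

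**Different risk in missing children.** Take 20% observed and 30% missing. The table shows 0.7 × 20% = 14%. The true rate is 14% + 0.3 × 20% × RR. For RR = 0, 0.5, 1, 1.5 and 2 this is 14%, 17%, 20%, 23% and 26%. The rule is right only at RR = 0. The observed-case 20% can be too high or too low.

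**Unequal missingness.** With 15% observed in both arms and 10% against 30% missing, the tables show 0.9 × 15% = 13.5% and 0.7 × 15% = 10.5%. The gap is spurious.

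**Unreturned 24-month ASQ-3, whole children.**

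| Arm | N | Missing | Black zone | SAP rule | Observed cases | Worst case |
|---|---|---|---|---|---|---|
| Retosiban | 49 | 14 | 7 | 7/49 = 14.3% | 7/35 = 20.0% | 21/49 = 42.9% |
| Atosiban | 43 | 13 | 6 | 6/43 = 14.0% | 6/30 = 20.0% | 19/43 = 44.2% |
| Placebo | 6 | 2 | 1 | 1/6 = 16.7% | 1/4 = 25.0% | 3/6 = 50.0% |

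**Referred but not assessed.** Take 49 screened, 10 black-zone and referred, 6 assessed, 2 scoring below 4, and 4 not assessed.
- Black-zone and referral endpoints: 10/49 = 20.4%, correct under the rule.
- BSID-III score endpoint, SAP rule: 2/49 = 4.1%.
- Unassessed children dropped: 2/45 = 4.4%.
- Unassessed children at the assessed rate: (2 + 4 × 2/6)/49 = 6.8%.
- Worst case: 6/49 = 12.2%.

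Dropping the screen-positive children hardly corrects the rate, so this endpoint needs bounds.

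**Composite.** Take 49 infants, 4 events and 10 unknown. The SAP rule gives 4/49 = 8.2%, which is the best case; the worst case is 14/49 = 28.6%. The known-status rate, 4/39 = 10.3%, is biased upward. One positive component keeps a child in as an event despite other blanks, while a child with only negatives and one blank leaves the denominator.

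**The case against.** The strongest case against is that the size is wholly assumed, the study is descriptive, development has ended, and the plan already limits or reveals the gaps. Families are contacted repeatedly and lost cases can be re-opened (Protocol 7.1.1). Collection may be extended for evaluations still in progress at 24 months (Protocol 3.1). SAP 7.2.3 tabulates reasons for no assessment and non-BSID-III delay, SAP 6.2 gives milestone counts, and listings show blanks. Table shells are a separate document, so the percentage denominator and the meaning of n in SAP 10.4.3 cannot be confirmed.

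This stands as a limit on size and visibility. It does not correct a percentage. Scoring missing children as non-events has meaning only if they are in the denominator, and none of the table titles in SAP 10.8.2 and 10.8.3 indicates observed cases or bounds.

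A reader might infer more than the documents support:
- **Every child without a BSID-III is mis-scored.** No. A child with a completed ASQ-3 and no trigger was not asked for one.
- **Unassessed referrals distort the black-zone and referral endpoints.** No. Those children are counted there.
- **A missed behavioural screen is scored as no ASD, ADD or ADHD in the composite.** That component is a diagnosis; a missed screen removes a route to referral.
- **A missed 24-month CHI erases hearing or vision loss.** The CHI is asked eight times, and earlier reports are followed up and medically confirmed (Protocol 6.2.1.1 and Confirmation of Parent-Reported Data).
- **The protocol predicts rising drop-out within 24 months.** The Appendix 1 remark belongs to the argument against continuing to 5 years.
- **Infants never enrolled are part of this problem.** That is a separate denominator question for the Infant Safety tables; the definition of missing does not clearly reach families who declined.

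**Conclusion.** The rule is wrong as written for the screening endpoints, the BSID-III score endpoints and the composite. Its direction is arithmetic and needs no assumption beyond missing children being in the denominator. Its size cannot be derived from the documents; the illustrations show only how it scales with missingness and with risk in the missing children. It lowers rates in every arm, so the documents do not show that it favours retosiban in the comparison. That depends on how missingness and risk differ by arm.

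For SAEs and newly diagnosed conditions the point is narrower: reading no report as no event is reasonable while a child is under observation, but not afterwards.

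**What to change.** Replace the rule in SAP 10.6.2 before unblinding, since SAP Section 8 allows no later change, and record the change there.

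1. **ASQ-3, M-CHAT-R/F and CBCL/1.5-5 endpoints:** divide by infants with a completed instrument at that time point. Show numbers missing and died by arm.
2. **Referral endpoints:** count every referred child, assessed or not. Divide by infants with a completed triggering screen plus any child referred by another route, which Protocol 3.1 allows.
3. **BSID-III score endpoints:** children with a completed ASQ-3 and no trigger are non-events. Show referred children without a BSID-III as unknown by arm, separating those with another evaluation from those with none. Make best-case and worst-case rates over all screened children the main display.
4. **24-month composite:** an event if any component is positive, with previously confirmed hearing, vision or other diagnoses carried forward. A non-event if every component is known negative, or not triggered after a completed screen or CHI. Otherwise unknown. Report all three counts by arm, with best-case and worst-case rates over all enrolled infants, and do not use the known-status rate alone.
5. **SAEs and newly diagnosed conditions:** treat no report as no event only during observed follow-up, read with the SAP 6.2 milestone counts.
6. **SAP 10.4.3:** define n as infants with data for that endpoint, and interpret ARIOS-collected endpoints from the ARIOS Safety (20.x) tables.

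The cost is SAP wording and changes to the table shells, with no new data. Denominators will vary by endpoint and time point, percentages will be somewhat higher, and bounds in the six-infant placebo group will be wide.

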#### 10.6.2.1. Handling of Missing/Partial Dates

Element	Reporting Detail
General	Partial dates will be displayed as captured in subject listing displays. No imputation will be applied.

## 10.7. Appendix 7: Abbreviations & Trade Marks

### 10.7.1. Abbreviations

Abbreviation	Description
ADaM	Analysis Data Model
AE	Adverse Event
ASQ-3	Ages and Stages Questionnaire version 3
BMI	Body mass index
BSID III	Bayley Scales of Infant Development 3 rd Edition
CBCL/1.5-5	Child Behaviour Checklist for Ages 1.5-5
CHI	Child Health Inventory
CSR	Clinical Study Report
eCRF	electronic Case Report Form
EDD	Estimated Date of Delivery
FMM	Finite Mixture Models
GA	Gestational Age
GSK	GlaxoSmithKline
ICH	International Conference on Harmonization of Technical Requirements for Registration of Pharmaceuticals for Human Use
IDSL	Integrated Data Standards Library
MedDRA	Medical Dictionary for Regulatory Activities
M-CHAT-R/F	Modified Checklist for Autism in Toddlers Revised with Follow-Up
RAP	Reporting and Analysis Plan
SAC	Statistical Analysis Complete
SAE	Serious Adverse Event
SAS	Statistical Analysis Software
SI	System Independent
SD	Standard deviation
SDTM	Study Data Tabulation Model
SOP	Standard Operating Procedure
SPTL	Spontaneous Preterm Labor

### 10.7.2. Trademarks

Trademarks of the GlaxoSmithKline Group of Companies	Trademarks not owned by the GlaxoSmithKline Group of Companies
NONE	NONMEM SAS WinNonlin

## 10.8. Appendix 8: List of Data Displays

A separate document for shells contains all table, listing and figures' (TLFs) for the planned final analysis.

### 10.8.1. Data Display Numbering

The following numbering will be applied for RAP generated displays:

Section	Tables	Figures
Study Population	10.1 to 10.4	
Safety	10.5, 20.5, 10.6, 20.6	
Other Analysis	10.7, 20.7, 10.8, 20.8, 10.10, 20.10, 10.11, 20.11	
Section	Listings	
ICH Listings	37, 38, 42 to 44	
Other Listings	39 to 41, 45, 46	

### 10.8.2. Study Population Tables

Study Population Tables					
No.	Population	IDSL / TST ID / Example Shell	Title	Programming Notes	Deliverable [Priority]
Subject Disposition					
10.1	Infant Safety		Infant Subject Disposition		
10.2	Infant Safety		Number of Infants Enrolled at Milestone		
Demographics					
10.3	ARIOS Safety		Infant Subject Demographic and Baseline Characteristics		
10.4	ARIOS Safety		Summary of Subject Race and Racial Combinations		
Medical Condition					
10.6	Infant Safety		Newly Diagnosed Chronic Medical Condition		
20.6	ARIOS Safety		Newly Diagnosed Chronic Medical Condition		

### 10.8.3. Safety Tables

Safety Tables					
No.	Population	IDSL / TST ID / Example Shell	Title	Programming Notes	Deliverable [Priority]
Adverse Events					
10.5	Infant Safety		Summary of Infant Serious Adverse Events		
20.5	ARIOS Safety		Summary of Infant Serious Adverse Events		
Neurodevelopment Assessments					
10.7	Infant Safety		Neurodevelopment Assessments (ASQ-3 and BSID-III scores) at 9, 18 and 24 Months		
20.7	ARIOS Safety		Neurodevelopment Assessments (ASQ-3 and BSID-III scores) at 9, 18 and 24 Months		
10.8	Infant Safety		Neurodevelopment Assessments (CBCL/1.5-5. M-CHAT-R/F, Cerebral Palsy or Behavioral Specialist) at 18 and 24 Months		
20.8	ARIOS Safety		Neurodevelopment Assessments (CBCL/1.5-5. M-CHAT-R/F, Cerebral Palsy or Behavioral Specialist) at 18 and 24 Months		
10.9	Infant Safety		Neurodevelopment Impairment at the End of Study (24 Months)		
20.9	ARIOS Safety		Neurodevelopment Impairment at the End of Study (24 Months)		
Congenital Anomaly					
10.10	Infant Safety		Summary of Congenital Anomaly		
20.10	ARIOS Safety		Summary of Congenital Anomaly		

**10.8.4. ICH Listings**

ICH Listings					
No.	Population	IDSL / TST ID / Example Shell	Title	Programming Notes	Deliverable [Priority]
Subject Disposition					
37	ARIOS Safety		Study Disposition		
Demographics					
38	ARIOS Safety		Demographic and Baseline Characteristics		
43	ARIOS Safety		Race and Racial Combinations		
Adverse Events					
42	ARIOS Safety		Infant Serious Adverse Events		
44	ARIOS Safety		Infant Deaths		

**10.8.5. Non-ICH Listings**

Non-ICH Listings					
No.	Population	IDSL / TST ID / Example Shell	Title	Programming Notes	Deliverable [Priority]
Medical Condition					
39	ARIOS Safety		Newly Diagnosed Chronic Medical Conditions		
Health Outcome					
46	ARIOS Safety		Infant Hospital Utilization		
Neurodevelopment					
40	ARIOS Safety		Neurodevelopment Assessments at 9, 18 and 24 Months		
41	ARIOS Safety		Neurodevelopment Assessments at 3, 4 and 5 Years		
45	ARIOS Safety		Developmental Evaluation
